**Table 1-1 Schedule of Activities**

Evaluations	Visit 1 Screening	Visit 2 Treatment Session #1	Visit 3 1-week Phone Follow-up1a,b	Visit 4 4-week Follow-up	Visit 5 8-week Follow-up	Visit 6 Treatment Session #2	Visit 7 1-week Phone Follow-up2a,b	Visit 8 12-week Follow-up/Exit for participants who received only 1 treatment session	Visit 9 20-week (12-week Follow-up/ Exit for participants who received 2 treatment sessions)	Notes
Visit Window	Day -7 to 1	Day 1 + 3		Day 28 + 10	Day 56 + 14	Day 56 + 14		Day 84 + 14	Day 140 + 14	
Visit Notes	Mandatory for all treatment areas	Mandatory for all treatment areas	Mandatory for all treatment areas	Mandatory for all treatment areas	Mandatory for all treatment areas.	Mandatory, by treatment area, if two treatment sessions. May occur same day as Visit 5.	Mandatory, by treatment area, if two treatment sessions	Mandatory, by treatment area, if only one treatment session	Mandatory, by treatment area, if two treatment sessions	See Section 7.2 for detail on information to be captured in Visit in case of study discontinuation
Informed Consent	X									
Inclusion/Exclusion	X	X		X	X	X		X	X	See Sections 5.1 and 5.2
Demographics	X									
Medical/Surgical History	X									
Concomitant Medications and procedures	X	X	X	X	X	X	X	X	X	See Section 6.5.1. At Visits 2 and 6, repeat if participant is treated over multiple days with > 24 hours between treatments.
Review Contraceptive Guidance	X	X	X	X	X	X	X	X	X	See Section 10.4, for WOCBP

Evaluations	Visit 1 Screening	Visit 2 Treatment Session #1	Visit 3 1-week Phone Follow-up 1a,b	Visit 4 4-week Follow-up	Visit 5 8-week Follow-up	Visit 6 Treatment Session #2	Visit 7 1-week Phone Follow-up 2a,b	Visit 8 12-week Follow-up/Exit for participants who received only 1 treatment session 	Visit 9 20-week (12-week Follow-up/ Exit for participants who received 2 treatment sessions) 	Notes
Urine Pregnancy Test	X	X				X				See Section 8.2.3, conduct before cryo-lipolysis treatments at Visits 2 and 6. At Visits 2 and 6, repeat if participant is treated over multiple days with > 24 hours between treatments.
Treatment site assessment		X		X	X	X		X	X	Conduct after cryo-lipolysis treatments and prior to massage at Visits 2 and 6.
Height	X									
Weight	X	X		X	X			X	X	Conduct before cryo-lipolysis treatments at Visits 2 and 6.
2D/3D Photography 	X	X		X	X			X	X	See Section 8.1.2, conduct before cryo-lipolysis treatment at Visits 2 and 6
Cryolipolysis Treatment		X				X				See Section 6
Pain Assessment		X	X	X	X	X	X	X	X	See Section 8.2.1

- 1a Phone follow-up should be scheduled 7 days from last treatment visit day in instance where participant received treatment session #1 over multiple days.
- 1b If, during this phone follow-up, any of the following local effects of erythema, bruising, swelling, and/or sensory alteration are reported related to treatment session #1, additional phone follow-up (or in-person visit if aligned to planned study visit) will be scheduled in accordance with the time criteria outlined in Table 2-1 for potential AE categorization.
- 2a Phone follow-up should be scheduled 7 days from last treatment visit day in instance where participant received treatment session #2 over multiple days.
- 2b If, during this phone follow-up, any of the following local effects of erythema, bruising, swelling, and/or sensory alteration are reported related to treatment session #2, additional phone follow-up (or in-person visit if aligned to planned study visit) will be scheduled in accordance with the time criteria outlined in Table 2-1 for potential AE categorization.
-  If a participant receives only one treatment session for specific body area(s), the participant will return at Visit 8 for the 12-week post-treatment session #1 follow up assessment and study exit. If a participant receives two treatment sessions to any or all treated body areas, participant will return at Visit 9 for 12-week post-treatment session #2 follow-up and study exit. If a participant receives only one treatment session to one specific body area and two treatment sessions to another specific body area, the participant will return for Visit 8 for 12-week follow-up for the body area that received only one treatment session and Visit 9 for 12-week follow-up of body area that received two treatment sessions. The exit for this participant is Visit 9.
-  For select study sites with 3D camera system, 3D images will also be taken at this time.
-  CSQ-Overall is to be administered only if patient received treatment to midsection (abdomen and flank) plus at least one additional specific body area. The CSQ-Overall should be completed at visit where at least 12-weeks have passed since the final treatment session for all the treated body areas. For example, if the participant receives only one treatment session for one specific body area but two treatment sessions for another specific body area, the CSQ-Overall should be administered at Visit 9 where all the treated areas will have undergone at least a 12-week post treatment period.
-  The CGPQ should be completed at visit where at least 12-weeks have passed since the final treatment session for all the treated body areas. For example, if the participant receives only one treatment session for one specific body area but two treatment sessions for another specific body area, the CGPQ should be administered at Visit 9 where all the treated areas will have undergone at least a 12-week post treatment period.
-  The 12-week post final treatment CPIQ should be completed at visit where at least 12-weeks have passed since the final treatment session for all the treated body areas. For example, if the participant receives only one treatment session for one specific body area but two treatment sessions for another specific body area, the CPIQ should be administered at Visit 9 where all the treated areas will have undergone at least a 12-week post treatment period.

Should it ever become necessary to remain isolated at home or to shelter-in-place per local, regional, or state orders, study visits may be impacted. This may include changes such as phone or virtual visits, visits at alternative locations, or changes in the visit frequency and timing of study procedures, among others. Additional details are provided throughout Section 8. Every effort should be made to ensure the safety of participants and site staff, while maintaining the integrity of the study. If visits cannot be conducted onsite due to travel restrictions or other pandemic or natural disaster-related reasons, follow the modifications provided throughout Section 8.

## 2. Introduction

The sponsor is investigating non-invasive subcutaneous fat reduction of the midsection (abdomen and flanks), upper arms, inner thighs, outer thighs, and submental area utilizing the CoolSculpting® Elite System with CoolSculpting® Elite applicators.

### 2.1. Study Rationale

The CoolSculpting device and applicators have been redesigned and updated (now known as CoolSculpting Elite) and therefore warrant further clinical investigation. While the technological characteristics and operating principals associated with the treatment remain unchanged from the predicate CoolSculpting device, the system has been enhanced to support the simultaneous use of two applicators, improving overall treatment efficiency. This innovation is reflective of physician feedback that suggests patients would prefer to have multiple treatment cycles performed at once rather than serial treatments in order to reduce the overall time of procedure and office visits. In addition, there is minimal data evaluating CoolSculpting treatment across multiple body areas that also captures patient satisfaction and treatment experience. This approach is reflective of real-world experience, where patients may be assessed for treatment on multiple body regions depending on areas of interest for noninvasive fat reduction. This study will collect meaningful data for the use of the CoolSculpting Elite system and CoolSculpting Elite applicators.

[REDACTED]. The purpose of the study described here is thus to further evaluate the safety, effectiveness, and patient satisfaction with the CoolSculpting Elite System in a more robust population and at both US and International sites. With the CoolSculpting Elite system, treatment applicators can be applied simultaneously while undergoing non-invasive subcutaneous fat reduction of the abdomen and flanks, upper arms, submental area, inner thighs, and/or outer thighs. The full applicator range will be utilized as applicable and per country clearances. In addition, patient reported outcome (PRO) instruments were developed and modified following additional qualitative research to better assess overall patient satisfaction comprising multiple body areas for treatment. This will be a global study to better inform CoolSculpting providers and patients worldwide about expected outcomes with the updated system and applicators, and to support a more patient-centric consultation and tailored treatment approach when multiple body areas are considered for treatment.

### 2.2. Background

CoolSculpting is a noninvasive, clinically proven fat-reduction treatment that selectively targets adipocytes using a patented cooling technology. The CoolSculpting mechanism of action is based on cryolipolysis, which works by cooling the subcutaneous tissue and preferentially targets adipocytes, leading to controlled elimination of adipocytes (Manstein 2008, Zelickson 2009). Adipose tissue appears more preferentially sensitive to cold injury than skin and other tissues (eg, skin, muscle, and nerve) and the crystallization of cytoplasmic lipids in adipocytes occurs at temperatures well above the freezing point of water (Epstein 1970, Beacham 1980, Manstein 2008).

In the United States, the CoolSculpting system first received FDA clearance in 2010 for noninvasive fat reduction in the flank followed by clearance for the abdomen in 2012 (Bernstein 2014). Further approvals were gained for visible fat bulges in the submental and submandibular area, thigh, along with bra fat, back fat, underneath the buttocks (also known as “banana roll”), and upper arm.

The CoolSculpting System was first CE marked for fat layer reduction in 2009. The clearance was for general fat layer reduction, without a specified treatment area. Up to now, the CoolSculpting system has gained clearance/approval in more than 70 countries.

The latest iteration of the CoolSculpting System (CoolSculpting® Elite) initially received US FDA clearance on 21 Jan 2020 (510k clearance) and was first CE marked in Europe in November 2020.

Several enhancements to the predicate CoolSculpting device were made to develop CoolSculpting Elite and accommodate simultaneous applicator use. For the vacuum applicators, the applicator cup was updated to provide a single assembled unit incorporating the contour, thus eliminating the need for the gasket. Consequently, the geltrap on some applicators was repositioned to the top of the applicator, and the latches and contour interface were removed from the applicator housing. The applicator umbilical is lighter and more flexible. Changes were also made to the predicate’s system control unit, vacuum, and chiller subsystems, hardware, and software to allow 1 or 2 treatments to be performed simultaneously. Simultaneous CoolSculpting Elite treatment consists of using Applicator A and Applicator B simultaneously. The applicator heating and cooling technology and method remain unchanged, utilizing the same thermoelectric coolers to achieve heating and cooling. The temperature feedback control mechanism remains the same and the device monitoring is through software monitoring.

The applicators are designed to treat most body areas, and there are 7 total body applicators that operate with the system (Curve 80, Curve 120, Curve 150, Curve 240, Flat 125, Flat 165, and Surface 150). The applicator consists of the applicator connector, the applicator umbilical, and the applicator head. All applicators except the Curve 80 and Surface 150 provide the ability to disconnect the handpiece from the umbilical.

While the CoolSculpting procedure is successful in reducing subcutaneous fat in various anatomical areas, patients often desire treatment in multiple body areas and typically more than one treatment session may be necessary to achieve desired results. Retrospective chart reviews indicate patients most commonly seek treatment for the abdomen and/or flanks and there is demand to treat other body areas beyond the midsection. In addition, physician feedback suggested that patients would prefer to have multiple CoolSculpting cycles performed at once in a single office visit to reduce the overall time of the procedures.

The present study would expand the eligible body areas that can be treated to be reflective of real-world treatment consultations. In addition, capabilities of the device to allow for simultaneous use of applicators would allow for treatment of multiple body areas in the same or reduced treatment time.

A previous global (ex-US) study by Braun et al evaluated PROs via the CSQ, CGPQ, and CPIQ-Midsection (CPIQ-M) (Study CMO-MA-PLS-0602). These were created de novo to address treatment satisfaction with the abdomen only, flank only, or abdomen and flank together.

The study demonstrated high levels of patient satisfaction after CoolSculpting treatment for the abdomen and/or flanks with up to 24 cycles that could be delivered over two treatment sessions (the primary endpoint being 89.6% of participants rating their satisfaction with the fat reduction procedure as “Satisfied” or “Very Satisfied” on the CSQ Item 1). Patients also reported significant improvement in psychosocial impact after CoolSculpting treatment as measured by the CPIQ-M as well as measures derived from the CGPQ (which were exploratory endpoints). The findings demonstrated that patients benefited from tailored and optimized treatment plans to achieve their aesthetic goals in the abdomen and flank areas.

Given that the present study will also allow treatment of the inner thighs, outer thighs, submental area, and/or upper arms, the available PRO instruments required modification and qualitative patient research for the additional body areas. It was also important to further develop and refine a generalizable questionnaire considering that all of the above body areas could be included in the treatment plan. Hybrid concept elicitation/cognitive debriefing interviews were conducted with 12 participants to confirm the concepts and test the clarity and understanding of the following PRO measures: Cryolipolysis General Procedure Questionnaire – (CGPQ), Cryolipolysis Psychosocial Impact Questionnaire (CPIQ), CSQ-Overall, CSQ - Midsection, CSQ - Upper Arms, CSQ - Inner Thighs, CSQ - Outer Thighs, and CSQ - Fat under Chin.

In addition, this study will evaluate effectiveness by correct identification of baseline vs post-treatment images of the treated body area(s) by at least two out of three blinded, independent physician reviewers. This is consistent with prior CoolSculpting studies where independent photographic review was used for the correct identification of pre- vs final post-treatment visit images as a marker of visible improvement. Three-dimensional images will also be obtained at select study sites that have access to 3D imaging system to assess volumetric measurements.

A participant question will be administered (Participant Evaluation of Noticeable Improvement) to assess whether participant starts to observe noticeable improvement at 4 weeks post-treatment #1 with CoolSculpting Elite on the treated body areas. [REDACTED]

Although there are numerous clinical studies that have been conducted with the prior CoolSculpting system, there have been a limited number of patients who have been studied with the CoolSculpting Elite device and applicators globally with treatment plans facilitating simultaneous applicator use and multiple body areas. There is a need to evaluate effectiveness, safety, and patient-centric outcomes related to the CoolSculpting Elite procedure as well as to generate data with the updated applicators across body areas.

## 2.3. Benefits and Risks

### 2.3.1. Benefits

Non-invasive subcutaneous fat reduction in the treatment area is anticipated to provide an aesthetic benefit and the use of this non-invasive system will eliminate the need for an invasive procedure that requires anesthesia or recovery time. Non-surgical fat reduction is one of the most frequent noninvasive cosmetic procedures and these procedures have become increasingly popular due to their convenience and accessibility. Patients who do not require significant fat reduction to achieve meaningful aesthetic results typically seek non-invasive fat reduction and body contouring procedures to avoid the pain, expense, downtime, and surgical risks associated

with invasive and minimally invasive procedures such as liposuction and laser-assisted liposuction. Over the last decade, the safety and effectiveness of cryolipolysis with CoolSculpting system for subcutaneous fat reduction has been well-established. In addition, patient satisfaction with cryolipolysis reported in the literature is consistently high. Advancements with the CoolSculpting Elite system in particular allow for dual applicator use that can shorten the overall time in clinic to complete treatment plan and provide for the opportunity to treat body areas simultaneously.

### 2.3.2. Risks

Although this study presents minimal risks to the participant, there is the potential for some risk when any cryolipolysis procedure is performed. The risks of using a CoolSculpting device can occur during and after the treatment and usually resolve within a few days. During the treatment, sensations of intense cold, numbness, tingling, cramping, pulling and mild pinching are expected due to the vacuum and cold temperatures to which the treatment area is subjected. Immediately after the treatment, it is common to see redness, firmness, bruising, swelling, as well as to have sensations of tingling, itchiness, numbness and pain on the treatment area. A sensation of fullness at the back of the throat may happen after a submental treatment.

Less commonly, the following side effects have been noted to occur after treatment, as outlined in the User's Manual: Paradoxical adipose hyperplasia that may require surgical intervention, late onset pain with typical onset several days after a treatment and resolution within several weeks, freeze burn that typically resolves without sequelae with proper care, hyperpigmentation and the additional events described in

Table 2-2.

The benefits of noninvasive fat reduction with CoolSculpting Elite treatment outweigh the risks.

Considering a pandemic or natural disaster, the benefit and risk to participants in this study has also been evaluated. Based on the limited information to date, no additional risk to study participants has been identified with the use of CoolSculpting Elite.

### Anticipated Device Effects (Local effects of the treatment)

There are known effects of the CoolSculpting procedure, previously recorded in prior studies as transient and/or temporary effects related to the cold application and/or vacuum pressure inherent in the treatment. Anticipated effects of treatment with the CoolSculpting device include:

- Inflammation of the subcutaneous fat layer, which is a desired effect of the procedure
- Sensations of coldness, stinging, burning, pinching, or pressure associated with placement of the applicator and the initiation of the cold treatment
- Known skin effects (eg, blanching, erythema, bruising, purpura, petechiae, swelling, discomfort, tenderness, or soreness at the treatment site, all mild to moderate in nature), which are temporary effects that resolve spontaneously shortly after the procedure
- Localized sensory changes (eg, numbness, tingling) at the treatment area spontaneously resolving without medical intervention within 12 weeks of the procedure

Anticipated device effects should not be reported as adverse events (AEs) unless the criteria below are met (Table 2-1).

### **When Anticipated Device Effects May Be Considered as Potential Adverse Events**

If an anticipated device effect is considered severe, prolonged, results in treatment interruption or discontinuation and/or requires medical intervention as outlined below, then the event will need to be evaluated as a potential AE.

In addition to the anticipated device effects that meet the criteria of reporting as an AE, other reported AEs with CoolSculpting treatment are presented in Table 2-2.

**Table 2-1      Guidance for Anticipated Device Effects**

Anticipated Device Effect	Criteria for AE Reporting	Description for AE criteria
Bruising	Severe or prolonged	Severe: Bruising (purple discoloration); purpura (purple-colored spots or patches); or petechiae (pin point red dots) that causes disruption to the participant's daily activities as assessed by the study investigator. Prolonged: Bruising lasting longer than 1 month.
Erythema	Severe or prolonged	Severe: Erythema (redness) that causes disruption to the participant's daily activities as assessed by the study investigator. Prolonged: Erythema lasting longer than 2 weeks.
Swelling	Severe or prolonged	Severe: The appearance of swelling (edema) that causes disruption to the participant's daily activities as assessed by the study investigator. Prolonged: Swelling lasting more than 1 month.
Discomfort during procedure	Interruption/ discontinuation of treatment, or requiring medical intervention	Discomfort reported during the procedure that is intolerable to the participant and results in an interruption or discontinuation of the procedure.
Discomfort post procedure	Requiring medical intervention	Significant discomfort, pain, cramping, tenderness, soreness, or muscle spasm following the procedure which results in medical intervention (unplanned physician visit and/or prescription pain reliever).
Sensory Alteration	Severe or prolonged	Severe: Sensory changes (pain, burning, stinging, hypersensitivity) with a severity warranting medical intervention or causing disruption to the participant's daily activities as assessed by the study investigator Prolonged: Sensory changes (numbness, tingling, burning sensation) that are prolonged (ie, lasting longer than 12 weeks).

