## 4. Study Design

### 4.1. Overall Design

This is a global, multicenter, multi-country, prospective, open-label, nonrandomized, interventional cohort, medical device post-marketing study evaluating the use of CoolSculpting Elite and CoolSculpting Elite applicators for noninvasive subcutaneous fat reduction of the abdomen, flanks, upper arms, inner thighs, outer thighs, and/or submental area in healthy volunteers. Participants will be enrolled at approximately 9 study sites.

Participants are eligible to receive up to two treatment sessions separated 8 weeks apart for the body areas eligible for treatment. Assessments will be completed 12 weeks after the final treatment session.

- If a participant receives only one treatment session for specific body area(s), the participant will return at Visit 8 for the 12-week post-treatment session 1 follow-up assessment and study exit.
- If a participant receives two treatment sessions for specific body area(s), the participant will return at Visit 9 for the 12-week post-treatment session 2 follow-up assessment and study exit.
- If a participant receives only one treatment session to a specific body area and two treatment sessions to another specific body area, the participant will return for both 12-week follow-up visits: Visit 8 for the 12-week post-treatment session 1 assessment of the body area that received only one treatment session and Visit 9 for the 12-week post treatment session 2 assessment of the body area receiving two treatment sessions; Visit 9 will also be the study exit visit for this participant.

Participant body areas selected for treatment during the study must be treated during the first treatment visit (Visit 2) and no new body areas may be treated at Visit 6. Participants planning to receive only one treatment session to a specific body area must have this treatment in Visit 2 during the first treatment session. Per investigator discretion, body areas identified for treatment may be treated simultaneously or sequentially. If sequential or simultaneous treatment is performed, there will be no difference in other treatment activities. Skin preparation, pain assessment, treatment site assessment, and post-massage, etc. will be identical in either case.

The study duration is up to approximately 20 weeks and consists of up to 7 scheduled study visits and 2 phone follow-ups per participant:

- Visit 1 (screening, Days -7 to 1)
- Visit 2 (treatment session #1, Day 1 + 3 days)

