Note: Treatment plan may be completed within a 7-day window from the day when the initial treatment is administered for this visit. The entire treatment session #1 plan for all the body areas selected for treatment must be completed within these 7 days.

- Visit 3 (1-week phone follow-up from last treatment day for participants who received treatment session #1 on any body area)

Note: If any of the following local effects of erythema, bruising, swelling, and/or sensory alteration are reported during Visit 3, additional phone follow-up (or in-person visit if aligned to planned study visit) will be scheduled in accordance with the time criteria outlined in Table 2-1 for potential AE categorization.

- Visit 4 (4-week follow-up after treatment session #1, Day 28 + 10 days)
- Visit 5 (8-week follow-up after treatment session #1, Day 56 + 14 days)
- Visit 6 (treatment session #2 [optional], Day 56 + 14 days, can be completed on the same day as Visit 5)

Note: Only body area(s) that were treated at Visit 2 and that require a second treatment session are to be treated at Visit 6. The treatment plan for specific body area(s) may be completed within a 7-day window from when the initial treatment is administered for this visit. The entire treatment session #2 plan for the body area(s) selected for a second treatment must be completed within these 7 days.

- Visit 7 (1-week phone follow-up from last treatment day for participants who received treatment session #2 on any body area)

Note: If any of the following local effects of erythema, bruising, swelling, and/or sensory alteration are reported during this Visit, additional phone follow-up (or in-person visit if aligned to planned study visit) will be scheduled in accordance with the time criteria outlined in Table 2-1 for potential AE categorization.

- Visit 8 (12-week follow-up/exit for participants with any body area that underwent only treatment session 1 at Visit 2, Day 84 + 14 days). If the participant receives only one treatment session to all body areas, this visit is also the study exit visit.

Note: If the participant receives only one treatment session to a specific body area and two treatment sessions to another specific body area, the body area that received only one treatment session will be assessed at this visit. The participant will return at Visit 9 for assessment of body area that received two treatment sessions and study exit.

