- Visit 9 (20-week follow-up/exit, corresponding to 12-week follow up for participants with any body area that underwent treatment session 2 at Visit 6, Day 140 + 14 days). If the participant receives two treatment sessions to any or all treated body areas, this visit is also the study exit visit.

Approximately 110 participants will be enrolled and approximately 96 participants are expected to complete the primary endpoint assessment based on an anticipated attrition rate of 12% or less.

During the course of the study, should it ever become necessary to remain isolated at home or to shelter-in-place per local, regional, or state pandemic-related orders, the sponsor will engage with study site staff in efforts to ensure the safety of participants, maintain protocol compliance, and minimize risks to the integrity of the study while trying to best manage participant continuity of care. This may include alternative methods for assessments (eg, phone contacts or virtual site visits) in agreement with the sponsor. In all cases, these alternative measures must be allowed by local regulations and permitted by the Independent Review Board (IRB)/Independent Ethics

Committee (IEC). Investigators should notify the sponsor if any urgent safety measures are taken to protect the participants against any immediate hazard.

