### **8.3.1. Time Period and Frequency for Collecting AE and SAE Information**

All AEs/SAEs will be recorded in the AE sections of the eCRF throughout the study periodTable 1-1 as observed or reported spontaneously by study participants.

Medical occurrences that begin before the start of study intervention but after obtaining informed consent will be recorded in the AE section of the eCRF and will be considered pretreatment AEs.

All SAEs will be recorded in the CRF and reported to the sponsor or designee using a SAE form immediately; and under no circumstance should this exceed 24 hours, as indicated in Section 10.5. The investigator will submit any updated SAE data to the sponsor within 24 hours of it being available.

Investigators are not obligated to actively seek all AE or SAE information after conclusion of the study participation. However, if the investigator learns of any SAE, including a death, at any time after a participant has been discharged from the study, and he/she considers the event to be reasonably related to the study intervention or study participation, the investigator must promptly notify the sponsor.

Pandemic infections should be captured as AEs. If the event meets the criteria for an SAE, then follow the SAE reporting directions per the protocol.

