**10.5.3 Post-treatment Clinical Assessment – Alteration in Sensation**

Post-treatment clinical assessment for alteration in sensation will be summarized by scale (1=mild, 2=moderate and 3=severe) for the following types of alteration in sensation by individual treated body area, combined treated body areas as specified in Section 6.0 and visit:

- Burning Sensation
- Numbness
- Tingling
- Other

Additionally, similar summary will be provided by treatment session and overall.

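### The 12-week threshold at which non-severe sensory alteration becomes an AE coincides with nominal exit and falls after some permitted exit dates, with no stated check past exit

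*Protocol*

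**What the plan says.** Protocol Section 2.3.2 keeps anticipated device effects out of AE reporting unless a Table 2-1 criterion is met. For sensory alteration there are two routes:

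- By severity, at any time: "Severe: Sensory changes (pain, burning, stinging, hypersensitivity) with a severity warranting medical intervention or causing disruption to the participant's daily activities".
- By duration: "Prolonged: Sensory changes (numbness, tingling, burning sensation) that are prolonged (ie, lasting longer than 12 weeks".

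Numbness and tingling are named only under the second route. The list of anticipated effects just before the table describes the expected course differently, as "spontaneously resolving without medical intervention within 12 weeks of the procedure".

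Section 4.1 sets the visits. Session 1 is "Visit 2 (treatment session #1, Day 1 + 3 days"; session 2 is at Day 56 with 14 days added; either session may be spread over a 7-day window. Exit after one session is Visit 8, Day 84 with 14 days added. Exit after two is Visit 9, for areas that "underwent treatment session 2 at Visit 6, Day 140 + 14 days".

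Section 4.1 and footnotes 1b and 2b of Table 1-1 call for extra phone follow-up, timed to Table 2-1, when sensory alteration is reported at the 1-week call. A substitute is allowed: "or in-person visit if aligned to planned study visit". After exit, Section 8.3.1 applies: "Investigators are not obligated to actively seek all AE or SAE information after conclusion of the study participation".

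On analysis, SAP 10.5.3 says: "Post-treatment clinical assessment for alteration in sensation will be summarized by scale (1=mild, 2=moderate and 3=severe". The breakdown is by body area, visit and session.

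**The concern.** The event is defined by lasting more than 84 days, and the last scheduled look is placed at about 84 days. A participant who is still numb at an exit visit on or before day 84 has an effect that is not yet an AE. The general duty in Section 10.5.4 to follow AEs to resolution does not attach to it, and Section 8.3.1 imposes no active search afterwards. Whether the case is ever classified then rests on the extra contact, which may not have been triggered or may already have been used up at the exit visit.

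Safety is one of the two study objectives, and AEs and ADEs are its first listed measure. Non-severe sensory change that persists beyond 12 weeks enters the SAP's TEAE and TEADE tables only if someone establishes that the threshold was passed. A missed case can only lower the count.

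**Working it through.** **Inputs** (Section 4.1 and Table 2-1): threshold more than 84 days; session 1 starts on Days 1 to 4; session 2 starts on Days 56 to 70; a session may run up to 7 days after its first treatment day; Visit 8 is Days 84 to 98; Visit 9 is Days 140 to 154.

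**Formula:** elapsed days = exit day − last treatment day. This is the longest an effect that begins with that treatment can have lasted by exit.

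**Nominal timing, the plan's own figure:** Visit 9: 140 − 56 = 84 days, exactly the stated 12 weeks. Visit 8: 84 − 1 = 83 days. Neither exceeds 84.

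**Range over permitted dates:**

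- One session: last treatment between Day 1 and Day 4 + 7 = Day 11. Shortest 84 − 11 = 73; longest 98 − 1 = 97.
- Session 2: last treatment between Day 56 and Day 70 + 7 = Day 77. Shortest 140 − 77 = 63; longest 154 − 56 = 98.
- Session 1 effects in two-session participants: 140 − 11 = 129 to 154 − 1 = 153, always above 84.

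If the 7-day window is read as ending six days after the first treatment day, the two lower bounds become 74 and 64.

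**Exit days that can meet the criterion** (first qualifying day = last treatment day + 85):

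| Exit visit | Last treatment | First qualifying day | Qualifying days of 15 |
|---|---|---|---|
| Visit 8 | Day 1 | 86 | 13 |
| Visit 8 | Day 4 | 89 | 10 |
| Visit 8 | Day 11 | 96 | 3 |
| Visit 9 | Day 56 | 141 | 14 |
| Visit 9 | Day 63 | 148 | 7 |
| Visit 9 | Day 70 | 155 | 0 |
| Visit 9 | Day 77 | 162 | 0 |

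**Share of permitted day combinations with exit beyond 84 days.** All combinations are weighted equally; this is an assumption, since actual visit dates are not given.

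- One session: 87% if treated on Day 1, 77% using the start window (46 of 60), 53% adding the 7-day spread (256 of 480).
- Session 2: 93% if treated on Day 56, 47% using the start window (105 of 225), 28% adding the spread (504 of 1,800).

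These describe the permitted calendar. They are not estimates of how many participants are affected.

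**The clock in a retreated area.** Take an area numb from Day 1, retreated on Day 56 and still numb on Day 140. By duration of the effect, 140 − 1 = 139 days, which passes the Table 2-1 threshold. Counted from the latest procedure, 140 − 56 = 84 days, which is still within 12 weeks and so still an anticipated effect. The two passages classify the same case differently.

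**The case against.** A reader might infer that participants leave at or before 12 weeks and that most prolonged numbness can never be counted. The documents do not support that. Both exit windows only add days, so with single-day treatment on the nominal day 13 of 15 Visit 8 days and 14 of 15 Visit 9 days exceed 84. Session 1 effects in two-session participants are observed for at least 129 days. Severe changes count at any time. Participants whose session 2 was rescheduled because of the US hold exit 84 to 98 days after it under the SAP.

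The shortest intervals also need Visit 9 held to its calendar window after a late session 2. The protocol repeatedly calls Visit 9 the 12-week follow-up after session 2, and footnotes 5 to 7 of Table 1-1 require at least 12 weeks since final treatment for three questionnaires. Sites may therefore delay the visit, although the stated window is Day 140 plus 14.

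The strongest counter-argument is that the protocol already has a mechanism. A contact timed to the Table 2-1 criterion should fall after 12 weeks, a visit too early to apply the criterion is arguably not aligned with it, and Section 2.3.2 places numbness immediately after treatment, so a lasting case would usually be reported at Week 1. This has force and keeps the gap small. It does not close it: the trigger is still the 1-week report, the planned visit nearest 12 weeks is exit itself, and nothing says the contact continues afterwards.

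A reader might also infer that the report would present sensory changes as resolved within 12 weeks. Nothing in the documents says so. Treatment sites are assessed at Visits 8 and 9, and SAP 10.5.3 summarises sensory findings by visit whatever their AE status, so presence at exit would be visible. What it specifies lacks duration, days since last treatment, and any link to the AE threshold.

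**Conclusion.** The point holds as a gap in AE ascertainment. The threshold of more than 84 days coincides with the nominal exit visit (83 or 84 days) and lies beyond some permitted exits: the interval is 73 to 97 days after one session and 63 to 98 after session 2. It cannot be met at any Visit 9 day if session 2 ends on Day 70 or later and Visit 9 keeps to Days 140 to 154. Because the supplementary follow-up depends on a Week 1 report, may be met by a planned visit and is not stated to outlast exit, AE or ADE status for the same persistent numbness can turn on scheduling, and the error runs toward under-reporting.

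This rests on the windows as written and on the last treatment day as the starting point. The share of participants symptomatic at exit is not given, so the effect on the reported rate cannot be sized. The correction is worth making because it is cheap.

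**What to change.** 1. In the Table 1-1 notes for Visits 8 and 9, require one phone contact for any sensory alteration still present in a treated area at exit, made once more than 12 weeks have passed since the last cycle in that area, whether or not it was reported at Visit 3 or 7. Record the outcome as AE or resolved.
2. Reconcile the anticipated-effects list in Section 2.3.2 with Table 2-1, and state the date from which the 12 weeks are counted in a retreated area.
3. In SAP 10.5.3, add sensory alteration ongoing at exit, with days since the last cycle in that area.

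The cost is a few phone calls, one protocol note, one clarified definition and one SAP table row. The downside is slightly later closure for those participants and possibly a few more reported AEs. Neither treatment nor the 12-week threshold changes.
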